## 1. Background

For many decades, sentinel lymph node biopsy (SLN) has been the standard of care in early breast cancer. In recent years the publication of the ACOSOG Z0011, (1, 2) showed that there was no advantage in performing axillary lymph node dissection (ALND) compared with not performing ALND, even when up to 2 sentinel nodes are positive, for patients receiving breast-conserving surgery, adjuvant radiotherapy, and medical treatment. In the study, 23.7% of the control group (ALND) patients had additional metastatic lymph nodes other than sentinel nodes. However, the axillary recurrence rate or DFS did not differ in the SLN only and control groups. (1) These findings raise questions about the need to remove sentinel lymph nodes, especially in patients who undergo breast-conserving surgery and whole-breast radiation.

The Sentinel Node versus Observation after Axillary Ultrasound (SOUND) trial was a prospective, multi-national noninferiority phase 3 study, which randomized patients with a negative preoperative axillary ultrasound (US) to SLN or no axillary surgery, prior to breast conserving surgery (BCS). (3) The primary focus of the study was to determine the oncological outcomes in patients with negative ultrasound results who avoided SLN. The results showed that there were no significant differences in survival or axillary recurrences. The cumulative incidence of isolated axillary recurrences at 5 years was 0.4% in the no-axillary surgery arm. In the whole cohort, only 2% of patients developed a distant relapse, 1% developed a local breast relapse, and 1% developed contralateral breast cancer. Interestingly, the diagnosis of other malignancies unrelated to breast cancer (approximately 3%) was the most frequent oncological outcome. (3)

Furthermore, only 13.7% of the patients treated with SLN had positive lymph nodes, with 11.7% having just one. Patients have only a likelihood of 0.6% of having four or more positive nodes, and therefore should not be treated with ALND in case a positive SLN is found.

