## **3. Study aims**

### Primary endpoint

Evaluation of the 3-year axillary recurrence rate

Evaluation of the 5-year invasive disease-free survival (iDFS)

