### Secondary endpoints

Evaluation of different type of radiation therapy

Evaluation of different type of systemic treatment

Evaluation of outcomes based on histologic stage and subtype

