#### ***Variables of interest***

- Center ID
- Patient ID
- Age (at surgery)
- Premenopausal/Postmenopausal
- Genetic risk factors (BRCA1, BRCA2, ATM, CHECK2, PALB2, PTEN, TP53, etc. )
- Personal risk factors (tobacco smoke, alcohol, physical inactivity, substance abuse, Obesity, etc.)

- Comorbidity (high blood pressure, DM, chronic lung disease, deficiency anemias, kidney disease and failure, weight, height, BMI, etc. )
- Side (Right-Left)
- Objective examination axillary (palpable/not palpable)
- Mammography (date, nodule or microcalcifications, size in mm)
- Ultrasound breast (date, size in mm)
- Ultrasound axillary lymph nodes (negative/doubtful)
- Cytology or histology of doubtful axillary lymph node (yes/no)
- MRI (YES/NO)
  - Date, size in mm
- Unicentric/multifocal/multicentric
  - By mammogram, US, MRI
- Breast core biopsy Histological:
  - Date
  - Histotype (NST, lobular, other type)
  - Grade (1,2,3)
  - ER: %
  - PgR: %
  - Her2 0, 1+, 2+(FISH/SISH/ISH no amplified), 2+(FISH/SISH/ISH amplified)  
3+
  - Ki67: %
- Date of surgery
- Type of breast surgery (Lumpectomy, oncoplastic surgery (round block, mammoplasty)
- Definitive histological result:
  - pT (mm)
  - Foci (u, m)
  - Histotype (NST, lobular, invasive + DCIS, other type)
  - Grade (1,2,3)
  - ER: %
  - PgR: %
  - Her2 0, 1+, 2+(FISH/SISH/ISH no amplified), 2+(FISH/SISH/ISH amplified)  
3+
  - Ki67: %

- RT (yes/no)
  - PBI (yes/no)
    - Date (start/end)
    - If yes, type (intracavitary brachytherapy, interstitial brachytherapy, external beam radiation treatment (EBRT), single fraction intraoperative radiation (IORT) )
    - Gy
    - number of fractions
  - WBI (yes/no)

If yes:

- Date (start/end)
- Type (VMAT, breath holding, IMRT)
- Gy
- Number of fractions
- Boost dose (yes/no)
  - If yes, Gy
  - If yes, how many fractions
- Adjuvant endocrine therapy (yes/no)
  - Type of endocrine therapy (tamoxifen, Letrozole, exemestane, anastrozole, other SERD)
- Adjuvant CT (yes/no)

Follow-up

- Date of last follow-up
- Recurrence: yes/no
- Type of recurrence: local/regional/locoregional/synchronous (regional + distant, local + distant, locoregional + distant)
- Date of recurrence
- Deceased: yes/no
- Date of death
- Cause of death

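### The follow-up variables have no field or date for contralateral or second primary cancer, although 5-year iDFS, which may count them, is a primary endpoint

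*Protocol*

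**What the plan says.** Protocol section 3 lists two primary endpoints. The second is "Evaluation of the 5-year invasive disease-free survival (iDFS"; no section lists its component events.

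Protocol section 5, Variables of interest, sets out what is collected. Its follow-up block holds the date of last follow-up, recurrence, and death with its date and cause. Recurrence is entered as "Recurrence: yes/no", with a date and with "Type of recurrence: local/regional/locoregional/synchronous (regional + distant, local + distant, locoregional + distant". The only laterality item, "Side (Right-Left", stands among the baseline variables. Some baseline items are left open-ended, for example "Personal risk factors (tobacco smoke, alcohol, physical inactivity, substance abuse, Obesity, etc"; the follow-up block has no such wording.

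Section 4.2 excludes bilateral breast cancer and previous malignancy, but these are entry criteria and do not concern new cancers. Section 6 provides for yearly follow-up over the first 5 years and adds no variable.

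The Background reports, for the cited randomised trial of sentinel node biopsy against observation, that "only 2% of patients developed a distant relapse, 1% developed a local breast relapse, and 1% developed contralateral breast cancer", and that "the diagnosis of other malignancies unrelated to breast cancer (approximately 3%) was the most frequent oncological outcome".

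**The concern.** A time-to-first-event endpoint can be built only from events that are recorded with a date. Contralateral breast cancer and second primary cancers are candidate components of iDFS, and the protocol's own Background treats them as oncological outcomes worth reporting. Yet the follow-up list gives a site no place to enter either one.

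Two things can then happen to a contralateral cancer. The site may leave it out, so that the patient stays event-free until another event, death or last follow-up. Or it may tick recurrence and choose a type that does not fit, and with no side recorded at follow-up the case could not be told apart from an ipsilateral relapse. With no written rule, centres may differ. A non-fatal second primary has no natural entry at all; a fatal one appears only as a death, dated at death and not at diagnosis.

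The SAP can still choose the definition of iDFS, but it cannot supply events and dates that were never collected. At stake is the level of a primary endpoint in a registry meant to describe outcomes when axillary surgery is omitted. The axillary recurrence endpoint and its sample size are not affected.

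**Working it through.** **Step 1. Candidate events against the follow-up block.**

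| Event | Where it can be entered | Date available |
|---|---|---|
| Local, regional or locoregional relapse | Own type | Yes |
| Distant relapse with local or regional disease | Synchronous type | Yes |
| Distant relapse alone | Recurrence yes, but no type fits | Yes, if entered so |
| Contralateral breast cancer | No field; recurrence yes with a type that does not fit | Only if entered so |
| Second primary non-breast cancer | No field | Only date of death, if fatal |
| Death | Own field, with cause | Yes |

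The distant-only gap concerns classification. It adds nothing to the figures below if sites enter such cases as a recurrence with a date.

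**Step 2. Inputs.** The protocol gives no figure for iDFS, so there is none to reproduce. Its sample size, used here only as a denominator, is 744 / (1 − 0.10) = 826.7, rounded up to the stated 827. From the Background: contralateral breast cancer 1%, other malignancies about 3%. Assumptions: these rates apply to the registry and are read as 5-year, invasive, non-overlapping events. The Background gives neither a time point nor invasive status for them.

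**Step 3. Size with nothing recaptured.** Overstatement of 5-year iDFS = sum of the proportions that count but are not recorded.

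- Neither event counts: 0.
- Contralateral only: 1.0 point; 827 × 0.01 = 8.3 patients.
- Contralateral plus non-breast primaries: 1.0 + 3.0 = 4.0 points; 827 × 0.04 = 33.1 patients.

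**Step 4. Recapture.** Let f be the share of these patients who still become events within 5 years, through death or an entry as recurrence. The gap is 1.0 × (1 − f) or 4.0 × (1 − f). The documents give no value for f, so the full range is shown.

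| f (assumed) | Contralateral only | With non-breast primaries |
|---|---|---|
| 0% | 1.00 | 4.0 |
| 25% | 0.75 | 3.0 |
| 50% | 0.50 | 2.0 |
| 75% | 0.25 | 1.0 |
| 100% | 0 | 0 |

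If every contralateral cancer is entered as recurrence but no non-breast primary is, 4.0 − 1.0 = 3.0 points remain (827 × 0.03 = 24.8 patients), provided non-breast primaries count.

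**Step 5. Overlap with other events.** Let S be iDFS from the recorded events alone. If events are independent, the gap is S × (1 − 0.99) for contralateral only, or S × (1 − 0.99 × 0.97) = S × 0.0397 for both. The Background rates for distant, local and isolated axillary relapse (2%, 1%, 0.4%) give S = 0.98 × 0.99 × 0.996 = 0.966, with no deaths. Taking S from 0.966 down to an assumed 0.85, to leave room for deaths, the gap is 0.97 to 0.85 points, or 3.8 to 3.4 points. The absolute size therefore depends little on S.

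**The case against.** The strongest objection concerns what is not shown. The list is headed as variables of interest and does not claim to be the full case report form, and the REDCap form is not available. Section 2 also promises insight into quality of life, for which the list has no item, so either the list is not exhaustive or there is a second gap. This stands as a limit: that events will be lost is not proven. But the list is the only statement of what is collected at follow-up, and a form built from it would lack these fields.

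It is also fair that the component definition of iDFS may sit in the SAP. Its absence from the protocol is therefore no part of this point; only data capture is.

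Sites could use the recurrence entry for contralateral cancer, just as this review assumes for distant-only relapse. That is why the recapture range runs to zero.

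Four stronger readings are tempting, and the documents do not support them.

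- **That 4 points is the expected bias.** Three of the four points require non-breast primaries to count, and no section says that they do.
- **That 1 and 4 points are upper bounds.** The registry admits any age and cT1-2, so its rates may be higher or lower than those cited.
- **That more than half of all iDFS events would be lost, or that the bias clearly exceeds sampling error.** Adding the Background rates gives 2 + 1 + 1 + 0.4 + 3 = 7.4 points, and 4.0 / 7.4 is 54%. That total leaves out deaths, which a disease-free survival endpoint would be expected to count, and the protocol gives no death rate. With an assumed 2 to 5 further points of deaths the share is 4.0 / 9.4 = 43% to 4.0 / 12.4 = 32%. Comparisons with a confidence interval built on the same total fail for the same reason.
- **That local relapse would be inflated and a radiation comparison distorted.** The secondary endpoint says only "Evaluation of different type of radiation therapy"; it names neither local relapse nor a comparison. The effect would also need contralateral cancers to be coded as local.

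Finally, the protocol sets no threshold, margin or test for iDFS, so no formal decision is shown to change. That is true, but the accuracy of a primary endpoint's estimate still matters in a descriptive registry.

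**Conclusion.** The concern holds as a data-capture gap and should be fixed. The follow-up block, as written, cannot record contralateral breast cancer or a second primary cancer with a date, and it has no distant-only type, while a primary endpoint may depend on the first two.

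The figures of about 1 point and about 4 points are illustrations. They rest on the cited trial's rates holding here over 5 years, on no recapture, and on the event types counting in iDFS; if neither type counts, the effect is 0. The gap in the list is plain on the page; its numerical effect is uncertain.

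**What to change.** In the follow-up block of the variable list and in the REDCap form:

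- add a yes/no field with date and invasive/non-invasive status for contralateral breast cancer;
- add the same for second primary non-breast cancer;
- add a distant-only code to type of recurrence;
- instruct sites to enter contralateral cancer in its own field and not as recurrence.

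Once these are collected, the SAP may decide which events count in iDFS.

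The cost is small. At most 827 × 5 = 4,135 yearly forms carry two extra tick-boxes, and at the cited rates the details would be needed for roughly 8 patients (contralateral) or 33 (both kinds). Section 7 says that use of REDCap has been requested, so the change may still come before the form is in use. The downside is a little more data entry at each yearly follow-up.

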#### **Statistical analysis**

A sample size calculation was performed to determine the number of participants required for a non-inferiority study comparing the experimental group to the general population. The reference axillary recurrence rate was set at 0.3% based on population data, while the expected recurrence rate in the experimental group was 1.0%, as reported in published studies. A significance level of 5% and a statistical power of 80% were used. The analysis determined that 744 participants were required. To account for potential dropouts and exclusions, the sample size was increased by 10%, resulting in a final adjusted sample size of 827 participants.

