## **6. Registration and therapy**

All patients with histologically confirmed invasive breast cancer and a negative axillary US who are candidates for omitting SLN biopsy or any axillary surgery will be informed about the possible participation in the study. The inclusion and exclusion criteria are verified by the investigator and written informed consent is obtained from the patient. Surgical treatment, pathological assessment and postoperative locoregional and systemic therapy should be conducted according to institutional and national standards. Since the OXYGENATE study is a non-interventional trial, the study sites do not deviate from their own institutional protocol at any timepoint. The follow up on patient status is conducted yearly during the first 5 years after surgery.

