## **7. Data management and analysis**

CUN conducts data management and analysis. All patients who fulfill inclusion criteria should be recorded in the study identification list that remains at the study site.

For further analysis pseudonymized data are either filled in the CRF by the study site and transmitted directly by the study site via eCRF. The eCRF platform that will be used for data management in the study is the institutional REDCap platform of the Clínica Universidad de Navarra, and a formal request for its use has already been submitted. REDCap (Research Electronic Data Capture) is a secure and standardized platform for collecting and managing clinical research data. This tool complies with data protection requirements and allows for the collection of pseudonymized information, ensuring that participants' data is not directly identifiable and that their confidentiality is properly protected.

Regarding the subsequent utilization of health-related data, it will be performed encrypted, and according to Article 26 HRO on data protection, the data will be transferred to the PI as established in the Data Transfer Agreement and analyzed at the Clínica Universidad de Navarra in Madrid. The data will be used exclusively for this project, and all confidential data will be securely protected.

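### The listed follow-up variables do not record whether a recurrence is axillary, so the first primary endpoint cannot be derived from them

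*Protocol*

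**What the plan says.** Section 3 of the protocol lists two primary endpoints. The first is "Evaluation of the 3-year axillary recurrence rate"; the second is 5-year invasive disease-free survival. The Statistical analysis paragraph sizes the study on the first: "The reference axillary recurrence rate was set at 0.3% based on population data", against an expected 1.0% in the registry cohort, and "The analysis determined that 744 participants were required".

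The follow-up block under Variables of interest (section 5) holds the date of last follow-up, recurrence yes/no, the type and date of recurrence, and death with its date and cause. The site of a recurrence is captured by one item: "Type of recurrence: local/regional/locoregional/synchronous (regional + distant, local + distant, locoregional + distant".

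Three other variables in that section mention the axilla: clinical examination, ultrasound, and cytology or histology of a doubtful node. All three describe the state before surgery.

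Section 6 adds only the schedule: "The follow up on patient status is conducted yearly during the first 5 years after surgery". Section 7 names the eCRF platform and adds no outcome item.

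**The concern.** The endpoint concerns one anatomical site, and the variable meant to feed it does not name that site. An axillary recurrence could be filed as regional, as locoregional, or as either of these with distant disease. In each code it would stand beside any other regional nodal event. The protocol does not say that regional means axillary, so each centre in an international registry must decide for itself.

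The direction of the error depends on a counting rule that the protocol does not state. Counting all four codes with a regional component can over-count axillary events. Counting only the plain regional code can miss axillary events that came with local or distant disease.

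The stake is the numerator of a primary endpoint that will rest on a handful of cases. Comparison with outside evidence suffers too. The benchmark in the Background is specific to the axilla ("The cumulative incidence of isolated axillary recurrences at 5 years was 0.4% in the no-axillary surgery arm"), and a count of regional events does not measure the same thing.

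**Working it through.** **1. Match the endpoint to the variables.**

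| Needed for 3-year axillary recurrence | In the follow-up list? |
|---|---|
| Start of follow-up | Yes, date of surgery |
| Date of event | Yes, date of recurrence |
| Censoring information | Yes, date of last follow-up and date of death |
| Event is in the axilla | No |

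Timing can be derived. The site cannot.

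**2. Count the codes.** There are six: local; regional; locoregional; regional + distant; local + distant; locoregional + distant. Four include a regional component. If codes are used in their plain sense, every axillary event falls among those four, so their total is an upper bound. Nothing in the list separates the axillary events within it.

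**3. Reproduce the planned sample size.** Inputs from the Statistical analysis paragraph: p0 = 0.003, p1 = 0.010, alpha 5%, power 80%. A one-sample test of a proportion, taken as two-sided, gives

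n = [(1.960 × √(0.003 × 0.997) + 0.8416 × √(0.010 × 0.990)) / 0.007]² = [(0.10719 + 0.08374) / 0.007]² = 743.97, so 744.

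With the 10% allowance, 744 / 0.9 = 826.7, so 827. Both figures match the protocol.

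**4. Expected events.** The planning rates carry no time horizon and are read here as 3-year rates.

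- At 0.3%: 744 × 0.003 = 2.2 events
- At 1.0%: 744 × 0.010 = 7.4 events

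**5. Weight of one misfiled event.**

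- Change in the rate: 1 / 744 = 0.134 percentage points
- Share of the planning gap: 0.134 / 0.7 = 19%
- Share of the expected count: 1 / 2.23 = 45% at 0.3%, and 1 / 7.44 = 13% at 1.0%

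**6. Illustration with exact (Clopper-Pearson) upper limits, n = 744.** The protocol fixes no interval method.

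| Events | Rate | Two-sided 95% upper limit | One-sided 95% upper limit |
|---|---|---|---|
| 2 | 0.27% | 0.97% | 0.84% |
| 3 | 0.40% | 1.17% | 1.04% |
| 7 | 0.94% | 1.93% | 1.76% |
| 8 | 1.08% | 2.11% | 1.93% |

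Between 2 and 3 events, one reclassified case carries the limit across 1.0%. Between 7 and 8 it does not.

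**7. If regional events stood in for axillary events.** The axillary share of regional recurrences is not in the protocol, so a range is assumed. The true axillary rate is set at 0.3%. The last column uses 6 or more events in 744 as an illustrative threshold.

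| Assumed axillary share | Apparent rate | Chance of 6 or more events |
|---|---|---|
| 100% | 0.30% | 2.6% |
| 90% | 0.33% | 4.0% |
| 70% | 0.43% | 10.4% |
| 50% | 0.60% | 29.1% |

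**The case against.** The strongest reply is that the gap is smaller than it looks. The four codes with a regional component contain every axillary event and come with dates, so the numerator is bounded. The axilla is the only regional nodal site that the protocol names. If nearly all regional recurrences are axillary, the over-count is close to nil. The under-count arises only if an analyst ignores codes that are regional by name, and a counting rule of that kind normally belongs in the statistical analysis plan. The eCRF may also hold more detail than the protocol's list.

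Several parts of this stand. The size of the over-count cannot be taken from the document. The 1.0% figure is a planning rate and not a margin, so crossing it carries no stated decision, and the crossing occurs at 2 versus 3 events but not at 7 versus 8. The Background benchmark already differs from the endpoint in horizon (5 years against 3) and in scope (isolated events only), whatever the coding.

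The main point survives. A statistical analysis plan can say which codes to count, but it cannot supply a site that was never recorded. An upper bound is not the stated endpoint. Defining regional as axillary would be a lighter change, but it would discard or mislabel recurrences at other nodal sites.

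**Conclusion.** The concern holds. With data collected exactly as the protocol lists them, axillary recurrence can be bounded from above but not identified, so the numerator of the first primary endpoint is undetermined.

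The endpoint is not lost. Section 7 keeps an identification list at each site ("All patients who fulfill inclusion criteria should be recorded in the study identification list that remains at the study site"), so recurrences could be queried later, although the protocol plans no such query.

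Each misfiled case shifts the estimate by 0.13 percentage points, on an expected 2.2 to 7.4 events. This assumes 744 evaluable patients and planning rates that apply at 3 years. The crossing of 1.0% and the figures by axillary share are illustrations, and the conclusion does not depend on them. It is limited to the variables listed in the protocol, because the eCRF is not shown. This should be fixed, preferably before recurrences accrue.

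**What to change.** In the follow-up block under Variables of interest, add a separate item for ipsilateral axillary recurrence (yes/no, with date). It is completed whenever a recurrence is reported, including locoregional recurrences and those synchronous with distant disease. Derive the first primary endpoint from this item, counting events within 3 years of surgery, and state whether an axillary event after an earlier recurrence elsewhere counts. Keep the existing type-of-recurrence item, so that axillary events with local or distant disease can be told apart from those without.

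The cost is one conditional eCRF field with a date, shown only for patients with a recurrence. If recurrences have already been entered, sites must complete the field for them retrospectively. The sample size (744, inflated to 827) and the yearly follow-up do not change.
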